1. INTRODUCTION

Obesity is a chronic disease characterized by an excessive body fat accumulation, which has a negative impact on health and affects the physical, social and emotional wellbeing. A double-blind study will be carried out using a weight loss program based on a low-fat, normoprotein, controlled ketogenic diet, followed by a metabolic adaptation process. During the weight loss process, psycho-emotional support and personalized physical activity supervision will be provided in order to modify lifestyle habits along with nutrition. In this study, supervision during 24 months of the weight lost is proposed to ensure the stability of the results obtained. In the initial phase where the diet process is fully controlled, the control group will receive the weight reduction program proposed by the WHO task force.

The weight loss program is developed according to the characteristics of each patient and includes medical control, dietary-nutritional supervision, introduction of a physical activity program and psycho-emotional support.

The primary objective of this study is to test the effectiveness, safety and security of this intervention method for weight loss and compare it with a conventional method for weight loss.

This document includes all the background information for the use of the so-called very low-calorie ketogenic diet, the hypotheses to be tested in this study, the methodology of how the objectives will be demonstrated and the statistical analyses used, the table of variables to be studied, the bibliography consulted and finally the materials used for data collection and management.

2. BACKGROUND.

Obesity is a chronic disease characterized by an excessive accumulation of body fat, which impacts health negatively and affects the physical, social and emotional wellbeing. It is a growing health problem with a high prevalence worldwide and a high impact in Mexico (1). According to a study conducted by the Food and Agriculture Organization of the United Nations (FAO), Mexico has become the country with the highest obesity rate, with 32.8% obese people, above the United States with 31.8% (2), such data definitely underestimates the problem in Mexico, since according to the National Health and Nutrition Survey (ENSANUT) 2018, 42.5% of men over 20 years old are overweight and 30.5%, are obese; while in women these figures correspond to 36.6 and 40.2%, respectively (3).

Higher total energy intake and sedentary lifestyles are most immediate contributors for the increase in the number of people with obesity. This is mainly attributed to an increase in the consumption of refined sugars, and to the consumption of a greater variety of foods with high energy content, without leaving aside the increase in commercial portions consumed (4).

The increase in the prevalence of obesity represents a growing public health risk, since obesity is not only an aesthetic problem or a body image appreciation problem, but also has a direct impact on health. Obesity is the underlying pathology of many chronic diseases, especially those related to lipid metabolism such as dyslipidemia, metabolic syndrome, or coronary and vascular diseases. In addition, obese patients also face other pathologies derived from weight gain, such as sleep apnea or osteoarticular disorders (5).

To effectively treat obesity, three goals must be met: to lose weight, to maintain the new weight, and to not regain the lost weight. The achievement of these goals is fundamentally based on three pillars: patient motivation, individualization of treatment, and realistic goals. Motivation is important because it has been proven that unmotivated patients show low adherence to the diet. (6) Treatment must be individualized, according to the patient's lifestyle and food preferences. For that purpose, it is necessary not only to regulate the diet, but also to encourage physical exercise and, if necessary, use medication. Setting realistic goals, agreed with the patient, allows the patient to become involved with the diet and facilitates adherence to it. (5).

Nowadays, there are a large number of diets available to treat and control obesity. One of the most commonly used by nutritionists is the hypocaloric diet. This type of diet consists of a daily caloric intake around 10% lower than the patient's basal metabolism, which normally represents an intake of between 800 and 1,500 kcal per day. To achieve this, in hypocaloric diets the consumption of the basic nutrients required by the body is reduced in a balanced way, maintaining their proportions: between 25% and 35% of fats, between 50% and 65% of carbohydrates, and between 10% and 20% of proteins. This type of diet has proven to be effective in short-term weight loss, but not in maintaining the weight loss (7). The possible causes of the low efficiency of hypocaloric diets in the long term are the lack of adherence to this type of diet, and the reduction of basal energy expenditure (4).

Due to the ineffectiveness of hypocaloric diets in the long term, a large number of diets have been developed that are based on the intake of different percentages of macronutrients that seek to optimize weight loss, especially in the long term. Among them is the protein diet, developed by Blackburn in 1976. This diet results in weight loss through a protein-rich diet and reduced intake of lipids and carbohydrates. In addition, as a consequence of the nutritional imbalance, the patient should receive supplementation with vitamins and minerals to ensure the supply of the micronutrients required by the body (8). The basis of the protein diet is the reduction of carbohydrate intake to a minimum. This ensures that in a 48-72 hour period, the body resorts to fats as an energy source, and ketone bodies are formed so that stored lipids are used as a source of energy. Studies on the efficacy of the ketogenic diet with very-low carbohydrate, high-protein and reduced lipid content show that it produces, not only a very rapid decrease in the weight of patients in the short term, but is also effective in the long term (9, 10).

So far, different variants of Blackburn's protein diet have been developed. Among them is the multidisciplinary Zélé program which, like the rest of the high-protein diets, is based on maintaining protein intake according to the calculated requirement, while reducing lipids and carbohydrate intake. However, this method does not only consist of weight loss by means of controlled ketosis, but also by patient re-education to promote changes in eating habits. . This program must be carried out under the supervision of a multidisciplinary group that includes a physician to control the possible side effects of ketosis, a nutritionist to supervise the nutritional habits and conditions, a

psychologist to strengthen and help maintain the patient's motivation for weight loss, and a physical trainer to adapt a personalized program for the preservation and strengthening of muscle mass.

The Zélé method consists of five stages: frank ketosis stage, mixed ketosis stage, transition stage, integral stage and maintenance. The ketogenic stage, in which a high-protein diet with high biological value (HBV) proteins is followed, supplemented with vitamins and minerals. In this stage, the expected weight is reduced by 70 to 80%, divided into frank ketosis and mixed ketosis, with a variable duration depending on the patient's initial weight and the kilograms to be lost, although for the purposes of the study a duration of between two and three months is proposed. In the transition stage, carbohydrates are incorporated with the purpose of leaving the metabolic state of ketosis. Later, in the integral stage, carbohydrates, natural proteins and fats are progressively incorporated, instilling in the patient the habits to achieve a balanced diet. In this stage, a loss of between 20% and 30% of the remaining excess weight is sought. Throughout the maintenance stage, with a supervised duration of two years, the patient is followed up and monitored to maintain the weight loss, with the advice of a team of dietitians and nutritionists.

The studies carried out to date with diets that are very-low in carbohydrates, high-protein and low in fat have demonstrated their efficacy in reducing weight both in the short and long term (9,10). There is increasing evidence that rapid weight loss, such as that achieved with this type of nutritional intervention, is associated with better long-term results, and initial weight loss has even begun to be considered as a predictor of long-term weight maintenance.(11,12,13,14) Furthermore, in 2012, George Blackburn himself acknowledged in an article that the tendency to use commercial rapid weight loss programs is appropriate, since they achieve better results.(15,16,17.)

The anecdotal experience obtained in daily practice with the Zélé method and products has shown great effectiveness in weight reduction, however, so far there is no scientific evidence of its efficacy or its medium and long term effects. By conducting a double blind study, our objective is to evaluate the efficacy and safety of this nutritional intervention for the reduction and maintenance of weight loss, due to the fact that it is possible, according to Zélé's food engineering system, to build a reduced carbohydrate diet under the same concept of Zélé's products for a controlled ketogenic diet, as well as to perform a 12 and 24 months follow-up of the cohort to assess its efficacy not only in the initial stages, but also during the 24-month follow-up. The aim of this study is also to evaluate patient adherence to treatment, which in most studies reports a dropout rate of over 40% (4). In addition,

the characteristics of weight loss and the preservation of muscle mass and strength and finally patient satisfaction with their treatment will be evaluated.

3. PROBLEM STATEMENT

Obesity is one of the biggest pandemics in human history. According to the WHO, in 2016, more than 1.9 billion adults aged 18 or older were overweight, of which, more than 650 million were obese. Overweight and obesity are defined as an abnormal or excessive accumulation of fat that can be detrimental to health.

Until the end of the 20th century, the health problems of the population in developing countries were related to their nutritional status, especially stunting in children and anemia in women of reproductive age. But all that has changed in just a few decades; the world has gone from a nutritional profile in which the prevalence of undernutrition more than doubles that of obesity, to the current situation in which there are more obese people in the world than underweight people. Obesity and overweight, once considered characteristic of affluent societies, are now on the rise in low- and middle-income countries, especially in urban areas, where the increase is particularly marked.

This evolution toward obesity affecting the entire population is occurring at a frightening speed. In Mexico City, for example, obesity in the urban adult population has risen from 16% in 2000 to 35.6% in 2018. By then, the urban child population between 5 and 11 years old with obesity or overweight had already reached 35%. As for the country as a whole, it is estimated that currently seven out of ten Mexicans are overweight and that one third of those affected can be considered medically obese (ENSANUT 2018). Obesity increases the risk of diabetes mellitus, cardiovascular diseases, obstructive sleep apnea-hypopnea, and some types of cancer are within the group of conditions that have shown a direct association. Currently, the condition in which obesity, as an independent risk factor, has the greatest impact is type II diabetes mellitus with its costly complications, such as blindness, amputation of limbs and the need for dialysis, so finding a method accessible to the general population that achieves the reduction or control of obesity rates could have an impact on the reduction of cases of obesity that progress to DM-II and thus even have an impact on the national health budget.

Therefore, we ask ourselves if a structured multidisciplinary program based on a normoprotein ketogenic diet low in fat and carbohydrates is effective, safe for short-term weight loss and allows to maintain weight loss in the long term.

4. JUSTIFICATION

Overweight and obesity have been associated with an increased risk of multiple diseases including cardiovascular conditions and DM-II. If a person already has type 2 diabetes and gains weight, it will be even more difficult for him or her to control his or her blood sugar level.

In Mexico we do not know the current status of cardiovascular diseases associated with obesity, but in relation to DM-II presents high incidence in the population, in this regard the National Health and Nutrition Survey (ENSANUT) in 2018 revealed that approximately 8.6 million Mexicans have diabetes mellitus, which we can associate with the increase in the rates of overweight and obesity, which in children aged 5 to 11 years is 35.6%, from 12 to 19 reaches 39.7% and in the adult population over 18 years 76.8% in women and 73% in men, which represents an increase of at least 3% between 2012 to 2018. As commented, obesity and overweight is one of the most important risk factors for triggering Diabetes Mellitus. Good nutrition is an indispensable tool for the good control of all chronic degenerative diseases such as diabetes. Nutritional management is one of the determining factors to improve the control of many of these chronic degenerative diseases, mainly DM-II and hyperlipidemia. It is imperative to mention that diabetes is one of the main causes of death and the tendency is that the figures continue to increase due to the high rates of obesity and sedentary lifestyle in the world. The implementation of diets that help to reduce weight will favor the control and improve the quality of life of these patients, since it will reduce the risk of complications, and will also help to improve their self-esteem and avoid depression. The results obtained in this study are expected to be disseminated in research forums and scientific journals, as well as a technical report for the company that finances the project.

The direct benefits provided to the study population will be close monitoring of their clinical and metabolic evolution, awareness of their nutrition and how it impacts their health. There is no evidence of risk compared to the benefit that the rapid and safe reduction will provide to the study

population and to all those subjects who will be managed in the future with the proposed nutritional intervention.

5. OBJECTIVES

5.1 *General Objective*

To evaluate differences in the response of weight, body composition and metabolic biochemical parameters among obese patients following a normoprotein low-fat controlled ketogenic diet compared to a balanced BIEM).

5.2 *Specific Objectives*

- Intra- and intergroup comparison of patient weight and BMI reduction between baseline and subsequent follow-up monitoring visits.
- To determine the percentage of patients with weight loss equal to or greater than 10% of initial weight and the time it took for patients to reach this figure.
- Evaluate the evolution of comorbidities associated with obesity (HT, hyperglycemia or diabetes, hypercholesterolemia, hypertriglyceridemia, apneas), control of clinical and analytical parameters and changes in medication during the weight loss process and during follow-up.
- To know the tolerability of the diet: Incidence of side effects during the development of the study,
- Safety of the intervention diet: appearance of analytical alterations, especially of the ionic profile, renal function and hepatic function, incidence of serious adverse events.
- Assess diet adherence and dropout rate and cause.
- To know patient satisfaction with the assigned nutritional program.

6. HYPOTHESIS

Assumption 1: **Weight Loss** .

H1: The use of the "Zélé method" (**Tx1**) allows a greater weight loss (*pp*) than a hypocaloric diet (**Tx2**) in the same time (*t*).

Assumption 2.

H2: Tx1 is safe and with low or no adverse effects.

Assumption 3. **Metabolic conditions**

H3: *pp* with Tx1 allows the regulation of metabolic syndrome and its components.

H4: The state of controlled ketosis that occurs with Tx1 does not change pH or raise blood lactate levels.

Assumption 4 . **Body Composition**.

H5. Tx1 will produce a selective loss of fat and preservation of muscle mass.

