Blood samples will be collected in Specialized Clinical Laboratories according to NOM-253-SSA1-2012 and the laboratory sample collection manual in force in each laboratory. A venous sample will be taken to determine Complete Blood Biometry, Blood Chemistry of 27 elements, Basic thyroid profile, Glycosylated

7.8 Measuring instruments.

With all the data, a database will be built in Excel MS®. Patient satisfaction will be measured with the Likert Scale, which consists of 5 possible answers per item: very satisfied, satisfied, indifferent, dissatisfied and very dissatisfied. (attached)

7.9 Statistical analysis.

Descriptive statistical tests will be performed establishing general and group measures, determining variability measures such as standard deviation and Confidence Interval, comparative inferential tests will be performed within and between groups, for quantitative variables it is proposed as an initial T-test, which will be contrasted according to the conditions of normality and homoscedasticity of the sample. For qualitative variables, χ^2 is initially proposed, which will be contrasted according to the same conditions; one-way ANOVA and repeated measures ANOVA will also be used. Microsoft Excel 365 and SPSS V 21

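### H3 and H5 are worded for the ketogenic arm alone and 7.9 makes no contrast decisive, so a before-after change shared by both diets could be reported as confirming them

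*Combined protocol and SAP*

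**What the plan says.** Section 6 states five hypotheses. H1 has a comparator: more weight loss with Tx1 "than a hypocaloric diet" (Tx2) over the same time. H3 and H5 have none. H3 holds that weight loss "with Tx1 allows the regulation of metabolic syndrome and its components"; H5 holds that "Tx1 will produce a selective loss of fat and preservation of muscle mass".

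Section 5.1 frames the same domains comparatively, with the ketogenic diet set against the balanced one: "To evaluate differences in the response of weight, body composition and metabolic biochemical parameters among obese patients". Among the specific objectives in 5.2, the only one that names both kinds of comparison covers weight and BMI: "Intra- and intergroup comparison of patient weight and BMI reduction between baseline and subsequent follow-up monitoring visits". The objective on comorbidities, the nearest to H3, names no comparator.

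Section 7.9 says that "comparative inferential tests will be performed within and between groups". For quantitative variables "it is proposed as an initial T-test", with one-way and repeated measures ANOVA also listed. No test is assigned to a hypothesis and no primary contrast is named.

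Three further points bear on this. Controls are later moved to the ketogenic diet, and no week is given (7.4). Follow-up biochemistry is triggered by weight-loss or ketone milestones (7.1). Bioimpedance is done during nutritional counselling, which is part of the frequent visits (7.1, 7.7).

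**The concern.** The comparator is active. Tx2 is set at 20% below basal expenditure (7.10.2), and under 7.1 patients on both treatments are seen weekly and receive nutritional, psycho-emotional and activity counselling. The background (section 2) accepts that hypocaloric diets work for weight in the short term, and section 4 expects weight-reducing diets to help control chronic disease. Some improvement in fat mass and metabolic measures is therefore to be expected in both arms.

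A before-after test in Tx1 cannot separate the effect of the ketogenic diet from weight loss by any diet, from counselling, or from regression to the mean. H3 and H5 as worded can nevertheless be answered by that test, and 7.9 supplies it. Because the between-group test is run too and neither is designated, the choice of which to report against H3 and H5 can be made after the results are seen. What is at stake is whether those two conclusions rest on the randomised comparison.

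**Working it through.** **The plan's own figure.** The only design figure is 56 cases and 32 controls, for 95% power with a 95% CI and 35% attrition (7.4). It cannot be reproduced, because no effect size, SD or response rate is given. The point does not depend on it; it only supplies sample sizes for the illustration.

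**Inputs.**
- Tx1 enrolled: 56 (7.4). After 35% attrition: 56 × 0.65 = 36.4, taken as 36.
- Tx2 enrolled: 32 (7.4). After 35% attrition: 32 × 0.65 = 20.8, taken as 21.
- Two-sided alpha 0.05, an assumption read from the 95% CI in 7.4.
- d, the true mean improvement in SDs of the change score, is assumed equal in both arms. The documents give nothing from which to estimate it, so a range is shown.

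**Step 1: before-after test in Tx1 alone.** Power = P(T > t), where t is the 0.975 quantile on n − 1 degrees of freedom and T is noncentral t with noncentrality d√n. The critical values are 2.030 for n = 36 and 2.004 for n = 56. For example, at d = 0.5 and n = 36 the noncentrality is 0.5 × 6 = 3.0, and the power is 0.83.

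| d (same in both arms) | n = 36 | n = 56 |
|---|---|---|
| 0.3 | 0.42 | 0.60 |
| 0.5 | 0.83 | 0.96 |
| 0.7 | 0.98 | >0.99 |

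These are the probabilities that a one-arm reading confirms the hypothesis when the diets do not differ.

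**Step 2: between-arm test on the same data.** With equal true changes, the two-sample t-test on change rejects 5% of the time, half of that in favour of Tx1. Simulation (40,000 trials per setting, d from 0.2 to 1.0, arms 56/32 and 36/21) gave 2.4% to 2.6% favouring Tx1. The rate does not depend on d.

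**Step 3: what the calculation covers.** It models a shared improvement, so it applies to H3 and to the fat-loss half of H5. Preservation of muscle is a claim of no change: there, a significant before-after fall would count against H5, and a non-significant one would not establish preservation. No figure is offered for that half.

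**The case against.** The strongest reply is that the comparison is already in the protocol. Objective 5.1 asks for between-diet differences in exactly the domains of H3 and H5, the sentence in 7.9 covers tests between groups as well as within them, and nowhere is it said that a hypothesis will be accepted on a within-arm test. All of that stands. It limits the point to a missing link between the hypotheses and the contrast that should decide them; it does not remove it, because neither 5.1 nor 7.9 assigns the between-arm test to H3 or H5.

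Two stronger readings are tempting, and the documents support neither.

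- A reader might infer that randomisation is discarded for H3 and H5. It is not: the randomised comparison is planned, but not made decisive.
- A reader might infer that the trial will often find Tx1 significant and Tx2 not, and call that a difference, helped by the unequal arms. With no true difference, the chance of that pattern is (power in Tx1) × (1 − power in Tx2). At d = 0.5 and 36/21 this is 0.83 × (1 − 0.59) = 0.34. But no section states such a decision rule. The figure also runs from under 1% to 37% over d = 0.2 to 1.0 and the two sets of sample sizes; at d = 0.5 with 56/32 it is 0.21. It is not a fair measure of the problem.

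**Conclusion.** The point holds in a limited form. H3 and H5 are out of step with objective 5.1, and 7.9 leaves open which of two planned tests decides them. If the Tx1 before-after test is used, equal improvement of 0.3 to 0.7 SD in both arms would be reported as confirmation with probability 0.42 to 0.98 (36 completers) or 0.60 to above 0.99 (all 56), against about 2.5% for a between-arm test.

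These probabilities rest on an assumed d, equal true change in both arms, normally distributed changes and two-sided alpha 0.05. The direction of the problem does not depend on the exact d or on the sample size. It concerns H3 and the fat-loss half of H5. It does not show that the between-arm analysis is absent, nor that the sponsor intends to rely on the within-arm test.

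**What to change.** - **Section 6:** reword H3 and H5 as Tx1-versus-Tx2 differences in change from baseline, in line with 5.1.
- **Section 7.9:** state that the between-arm contrast at one named week, before any control crosses over, decides H3 and H5. Label within-group tests descriptive and draw no conclusion on a hypothesis from them.
- **H5 and the blood pressure component of H3:** the named week can be one of the visits already planned, so no extra measurement is needed.
- **Laboratory components of H3:** because biochemistry follows weight-loss and ketone milestones, the arms would be sampled at different times. Either tie one already planned draw to a common week in both arms, or report these laboratory before-after changes as descriptive only. The capillary glucose in 7.7 does not fill the gap, since 7.6 defines glucose on a fasting blood sample.

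**Cost.** Wording in sections 6 and 7.9, and possibly one laboratory draw re-timed. H3 and H5 also become harder to confirm. By the normal approximation, 80% power between arms needs a difference of (1.960 + 0.842) × √(1/56 + 1/32) = 0.62 SD of change with all patients, or 2.802 × √(1/36 + 1/21) = 0.77 SD with completers. That is the price of attributing the change to the diet.
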